4. SUMMARY/SYNOPSIS

| Short Title | Pacemaker therapy for drug-refractory symptoms in | | | | | |
|-----------------------|--|--|--|--|--|--|
| | mid-cavity HCM | | | | | |
| Methodology | Randomised controlled double-blinded cross over | | | | | |
| | trial | | | | | |
| | | | | | | |
| Research Sites | Barts Heart Centre, Barts Health NHS Trust | | | | | |
| Objectives/Aims | Primary | | | | | |
| | Phase IIb trial to test the efficacy of distal ventricular | | | | | |
| | pacing for pressure gradient reduction across the site | | | | | |
| | | | | | | |
| | of mid-cavity obstruction. | | | | | |
| | Secondary | | | | | |
| | To test the feasibility of a double-blind cross-over | | | | | |
| | study design in this cohort, collecting descriptive data | | | | | |
| | on various symptom, imaging and performance | | | | | |
| | markers, allowing establishment of baseline | | | | | |
| | | | | | | |
| | statistical data for the design of a larger outcomes- | | | | | |
| | based clinical trial. | | | | | |
| Number of | 25 | | | | | |
| Participants/Patients | | | | | | |
| Main Inclusion | a) Male or female, >18 years. | | | | | |
| Criteria | b) Referred for PPM +/- ICD implantation for | | | | | |
| | either primary prevention of sudden cardiac | | | | | |
| | death or other indications such as heart block | | | | | |
| | or obstructive physiology. | | | | | |
| | or obstructive physiology. | | | | | |
| | c) HCM patients with a mid-cavity gradient of ≥30 | | | | | |
| | mmHg demonstrated by echocardiography | | | | | |
| | and gradient confirmed by cardiac | | | | | |
| | catheterisation at rest or with isoprenaline | | | | | |
| | provocation. HCM morphology confirmed by | | | | | |
| | | | | | | |

<<Version 9>> <<09/11/2017>> <<Pacemaker therapy for drug-refractory symptoms in mid-cavity HCM

| | cardiac MRI. | | |
|--------------------|--|--|--|
| | All patients should be taking maximum tolerated doses of beta blockers or verapamil with or without disopyramide. | | |
| | e) Symptoms refractory to optimum medical therapy as above, for example breathlessness, chest pain, dizziness, or syncope. | | |
| Exclusion Criteria | a) Patients with multi-level obstruction, i.e. across the mid-cavity and outflow tract. | | |
| | b) Patients with moderate or severe valvular stenosis or regurgitation due to primary valvular disease | | |
| | c) Patients with untreated symptomatic coronary disease. | | |
| | d) Patients in atrial fibrillation at the time of implantation. | | |
| | e) Pregnancy | | |
| | f) Renal failure with eGFR <20mL/min | | |
| | g) Any patient not suitable in the clinician's opinion | | |
| | h) Any patient who is for whatever reason is not expected for more than one year | | |
| | i) Patients unable to provide informed consent | | |
| Statistical | All patients completing the initial invasive pacing | | |
| Methodology and | study will be eligible for the primary analysis. The | | |
| Analysis | secondary aim is to collect descriptive data regarding | | |
| | the feasibility of a cross-over design trial and | | |
| | corresponding methods used to assess symptoms | | |

| | and physical performance in this cohort. A statistical | | | | | |
|---------------------|--|--|--|--|--|--|
| | analysis of the results will be undertaken at the | | | | | |
| | completion of the study. Descriptive statistics will be | | | | | |
| | collected in the form of mean \pm standard deviations, | | | | | |
| | and these outputs will form the statistical basis for a | | | | | |
| | larger multi-centre RCT. | | | | | |
| | | | | | | |
| Proposed Start Date | December 2017 | | | | | |
| Proposed End Date | 1 st June 2021 | | | | | |
| Study Duration | Total duration: 41 months | | | | | |
| | Recruitment duration: 28 months (ending March 2020) | | | | | |

5. INTRODUCTION

5.1 BACKGROUND AND RATIONALE

5.1.1 Hypertrophic cardiomyopathy

Hypertrophic cardiomyopathy (HCM) is the commonest familial heart disease, with a prevalence of approximately 0.2% across multiple ethnicities.¹ It is characterised by left ventricular hypertrophy (LVH) in the absence of another disease process accounting for the magnitude of hypertrophy present.² Many patients are asymptomatic for decades, but may present with cardiac arrhythmias or with debilitating symptoms including chest pain, dyspnoea, dizziness and fatigue.³ In severely symptomatic HCM, exertional intolerance may be similar to that of advanced heart failure.

5.1.2 Obstructive HCM

The presence of obstruction to left ventricular (LV) emptying in systole is frequently detected in patients with symptomatic HCM. LV obstruction <<Version 9>> <<09/11/2017>> <<Pacemaker therapy for drug-refractory symptoms in mid-cavity HCM >>

contributes to symptoms and prognosis, and the presence and magnitude of obstruction dominates clinical decision making.⁴ In the 'classical' variant of obstructive HCM, the systolic and closed mitral valve moves toward the hypertrophied interventricular septum. Mitral - septal contact (systolic anterior motion [SAM]) results in a dynamically developing LV outflow tract obstruction (LVOTO) and mitral regurgitation. In a less common HCM variant (up to 10%),^{5, 6} a dynamic intracavity obstruction develops as a consequence of hypertrophy and apparent hypercontractility at the level of the papillary muscles causing LV mid-cavity obstruction (LVMCO).⁷ LVMCO is not associated with mitral regurgitation or SAM and is often missed at echocardiography. This is due to the distal chamber being outside the sector of two-dimensional imaging as a result of foreshortening of the imaging plane, or unclear imaging due to echoes from lung tissue.⁸

5.1.3 Pathophysiology of LVMCO

In patients with LVMCO, circumferential mid-systolic muscular apposition in the LV cavity creates two distinct chambers, proximal and distal, separated by a zone of apposition.⁹ During systolic ejection, the 'mid-cavity' zone of apposition impedes or completely obstructs the flow of blood from apex to base and a pressure gradient develops between the proximal 'sub-aortic' LV and the distal 'apical' LV¹⁰ The abnormally high intracavity pressure that develops in the apical chamber, and the increased LV wall stress, may be associated with reduced regional myocardial perfusion and ischaemia.¹¹ Over time, patients with LVMCO have been shown to be at higher risk of developing segmental or diffuse hypokinesia,¹² subsequent formation of an apical aneurysm,¹¹ and other clinically unfavourable consequences such as ventricular tachycardia (VT) have been reported.¹³

As a direct result of the risk of VT, many LVMCO patients receive device therapy with implantable defibrillators. It is in such patients that symptomatic benefits of ventricular pacing have been detected.

5.2 Therapeutic options for patients with LVMCO

Barts Health NHS Trust

Patients with LVMCO are reported to suffer from significant morbidity, with around 50% having severe symptoms,⁶ and data suggest this sub-group have a poor prognosis.¹³ β blocking agents and/or verapamil may improve congestive symptoms and functional limitation, although with little evidence that they are able to reduce intraventricular gradients with any consistency.⁹ If β-blockers alone are ineffective, disopyramide (a class IA anti-arrhythmic drug), can reduce the degree of LV outflow obstruction and improve exercise tolerance.¹⁴ However, approximately half of LVMCO patients have been reported to be refractory to medical therapy.⁶ leaving few other treatment options. The invasive procedures of alcohol septal ablation (ASA) and surgical myectomy have limited evidence supporting their routine use in LVMCO and are technically challenging.9

Notably, the main prognostic intervention is device implantation with an implantable cardioverter defibrillator (ICD) for primary prevention of sudden cardiac death, having the option of dual chamber pacing (PPM +/- ICD).

5.3 Ventricular Pacing for LV Obstruction: Rationale

5.3.1 Right ventricular pacing as a therapeutic option in LVOTO

Patients with the more common LVOTO have several invasive treatment options to consider should optimum medical therapy fail to relieve their symptoms. The well-established septal reduction therapies of surgical myectomy and percutaneous alcohol septal ablation (ASA) have had similar success in reducing pressure gradients across the left ventricular outflow tract and reducing symptoms.¹⁵ Previous studies have suggested a role for dual chamber permanent pacemaker (PPM) therapy from the right ventricular apex for LVOTO gradient reduction and symptomatic relief for HCM patients,¹⁶ with long term maintenance of such benefits reported.¹⁷ A recent Cochrane review found that the improvement in both physiological measure and symptoms has since been found to be variable and subject to a placebo effect,¹⁸ vet the apparent placebo effect of the invasive procedure of PPM insertion is surely of similar level to the arguably more invasive ASA or myectomy procedures.¹⁹

5.3.2 Right ventricular pacing as a therapeutic option in LVMCO

<<Version 9>> <<09/11/2017>> <<Pacemaker therapy for drug-refractory symptoms in mid-cavity HCM >>

In patients with MCO and drug-refractory symptoms, however, the therapeutic options are far more limited as ASA and surgical myectomy may be unable to target the affected area of the LV. Dual chamber pacemaker therapy from the right ventricular apex has, in small numbers of patients been shown to reduce the pressure gradient across the site of obstruction in the mid-cavity and provide symptomatic relief, with a trend towards increased exercise tolerance.⁷

5.3.3 Left ventricular pacing as a therapeutic option in LVMCO

Recently, several case studies have been published that demonstrate pacing from the left ventricular free wall, via the coronary veins, has yielded better reduction in LVOTO gradient compared to pacing from the right ventricular apex.²⁰ Furthermore, LV and biventricular pacing appeared to cause reverse LV remodelling with a reduction in LV mass.²¹ Our own pilot data has demonstrated that pacing from the left ventricle via the distal middle cardiac vein may have clinical application in individuals with LVMCO also. In order to ascertain the optimal pacing site for acute gradient reduction, individuals are paced from the RV apex, then from the LV via the distal middle cardiac vein. It is our experience that acute gradient reduction is seen during distal RV ventricular pacing (by 59±36 mmHg), with a further reduction in gradient when pacing from the distal middle cardiac vein (by 66±26 mmHg).

5.4 Rationale and Risks/Benefits

The potential risk associated with pacemaker implantation is very small, however there are several small risks of infection (less than 1 in 100), air leak from a lung (1 in 100), and blood clot in the arm (1 in 50). These figures are from national databases, and our specialist Heart Centre has expert skill and a wealth of experience in implanting devices. Therefore, we estimate these risks to be even lower, having had no tension pneumothorax in the last year.

The length of each treatment phase is longer than previous pacemaker studies at 24 weeks in order to account for any wash-out periods for symptoms (where the participant still feels the effects of the treatment / nontreatment into the next phase of the study). This has historically been a

criticism of pacemaker studies in cardiomyopathy with a cross-over trial design. The time necessary for wash-out effects to no longer be experienced is unknown, therefore we have used a conservative approach and doubled the treatment / non-treatment arms to the 24 week duration.

6. TRIAL OBJECTIVES

6.1 Primary and secondary objectives and endpoints

6.1.1 Primary objective:

To test the efficacy of distal ventricular pacing for pressure gradient reduction across the site of mid-cavity obstruction.

6.1.2 Secondary objective:

To test the feasibility of a double blind cross-over study design in this cohort, collecting descriptive data on various symptom, imaging and performance markers, allowing establishment of baseline statistical data for the design of a larger outcomes-based clinical trial.

6.1.3 Primary Endpoint

Change in invasive gradient measured by intracardiac catheter during distal ventricular pacing (mmHg).

6.1.4 Secondary Endpoint

Feasibility of patients completing two arms of a cross-over trial design, and the corresponding performance tests and symptomatic assessments

6.2 Null Hypothesis

There will be no significant difference in mid-cavity obstructive gradients during ventricular pacing and normal sinus activation of the ventricle by invasive catheter measurement during pacemaker implantation.

7. METHODOLOGY

7.1 Inclusion Criteria

>>

a) Male or female, >18 years.

- b) Referred for PPM +/- ICD implantation for either primary prevention of sudden cardiac death or other indications such as heart block or obstructive physiology.
- c) HCM patients with a mid-cavity gradient of ≥30 mmHg demonstrated by echocardiography and gradient confirmed by cardiac catheterisation at rest or with isoprenaline provocation. HCM morphology confirmed by cardiac MRI.
- All patients should be taking maximum tolerated doses of beta blockers or verapamil with or without disopyramide.
- e) Symptoms refractory to optimum medical therapy as above, for example breathlessness, chest pain, dizziness, or syncope.

7.2 Exclusion Criteria

- a) Patients with multi-level obstruction, i.e. across the mid-cavity and outflow tract.
- **b)** Patients with moderate or severe valvular stenosis or regurgitation due to primary valvular disease.
- c) Patients with untreated symptomatic coronary disease.
- d) Patients in atrial fibrillation at the time of implantation.
- e) Pregnancy.

>>

- f) Renal failure with eGFR <20mL/min.
- g) Any patient not suitable in the clinician's opinion.
- h) Any patient who is for whatever reason is not expected for more than one year.
- i) Patients unable to provide informed consent.

7.3 Study Design / Plan – Study Visits

This is a single centre, prospective Phase IIb study, with primary outcome assessed during device implant. Secondary aims assess the feasibility of a randomised controlled double-blind crossover design with one year follow-up in this patient population. Potential participants will be identified by the patient's clinician team at consultant or registrar level. With the patient's permission, their details will be given to the research team who will make secondary contact with the patient to discuss the study in more detail and give appropriate study literature, and offer the patient the opportunity to take part in the study. There will be a minimum of 24 hours between the study explanation and the taking of informed consent. Possible participants will then attend for informed consent and baseline assessment by a researcher over one encounter. The patient will then attend for device implantation and invasive haemodynamic pacing study as part of their standard care. Patients will then have two additional study visits to hospital at 24±4 weeks (for symptom / exercise testing and cross-over) and 48±4 weeks (for symptom / exercise testing and conclusion of trial). The length of each treatment phase is longer than previous pacemaker studies at 24 weeks in order to account for any wash-out periods, which have historically been a criticism of cross-over trial designs.

NHS Trust 7.4 Study Scheme Diagram Patient screened in Inherited Cardiovascular Conditions Clinic and referred to researcher **Clinic visit** Confirmation of inclusion / exclusion criteria Key Research Study explained to patient by researcher and given all appropriate study documentation Clinical Patient declines participation Patient agrees to be participant Patient followed up in clinic Pre-implant Kansas City / SF36 questionnaire visit Pre-implant symptom and blood assessment Brain Natriuretic Peptide (BNP) test 6-minute walk test Pre-implant exercise assessment Exercise Echo and CPEX CMR (ideally within 6/12 prior to Pre-implant imaging assessment consent) implant visit Pacemaker Haemodynamic study and pacemaker implant Double-blind randomisation to treatment / nontreatment End of Follow-up and cross 24±4 weeks in non-treatment arm (back-up) 24±4 weeks in treatment arm (active) over visit **Cross-over** Double-blind symptom, exercise and BNP assessment as above with device reprogramming 24±4 weeks in treatment arm (active) 24±4 weeks in non-treatment arm (back-up) crial visit Symptom, exercise and BNP assessment as above (conclusion of study)

Barts Health

<<Version 9>> <<09/11/2017>> <<Pacemaker therapy for drug-refractory symptoms in mid-cavity HCM

8. STUDY PROCEDURES

8.1 Recruitment setting

This study will take place in a tertiary care cardiology department in collaboration with Queen Mary University of London. All members of the study research team will hold substantive or honorary contracts with their hospital institution.

8.2 Screening and Recruitment

Patients considered for study inclusion will be invited to join during their clinic appointment, after an explanation of the study.

They will be provided with a complete description of the study protocol and the benefits and risks involved. The interested patient will undergo screening procedures listed below.

8.3 Informed Consent

Written and verbal versions of the Participant Information and Informed Consent will be presented to potential participants detailing: the exact nature of the study; what it will involve for the participant; the implications and constraints of the protocol; the known side effects and any risks involved in taking part. It will be clearly stated that the participant is free to withdraw from the study at any time for any reason without prejudice to future care, and with no obligation to give the reason for withdrawal. The participant will be allowed as much time as wished to consider the information, and the opportunity to question the Investigator, their GP or other independent parties to decide whether they will participate in the study. Potential participants will be given at least 24 hours to consider taking part in the study.

<< Version 9>> << 09/11/2017>> << Pacemaker therapy for drug-refractory symptoms in mid-cavity HCM >>

Eligibility of potential participants will be re-checked by pre-defined inclusion/exclusion criteria (see 7.1 and 7.2 for details) at the time of consent. Written informed consent will be obtained by an investigator who is familiar with the study protocol and procedures and listed on the study delegation log. The participant must personally sign and date the informed consent forms, which will be witnessed by the investigator who will also sign and date before any specific procedures are performed. A copy of the signed informed consents will be given to the participant, with one copy up-loaded electronically to the Care Records System and a paper copy to the patient's notes. The original signed forms will be retained securely at the study site in the trial master file. The participant will then be formally "registered" and given a study specific ID.

8.4 Randomisation, blinding and code-breaking

A trial randomisation service (such as https://www.sealedenvelope.com or www.randomize.net) will be used to assign participants to one of the cross over arms initially.

8.5 Baseline Assessments

8.5.1 Pre-pacing study assessment (several of these tests are standard pre-device implant care, denoted by SC. Research activity denoted by RES)

a) Symptomatic assessment with SF36 and Kansas City Cardiomyopathy questionnaires and determination of New York Heart Association (NYHA) functional class. (RES)

b) Venous blood sample taken (SC), BNP test (RES)

6 minute walk test (6MWT) performed to assess baseline exercise C) tolerance. (SC)

<< Version 9>> << 09/11/2017>> << Pacemaker therapy for drug-refractory symptoms in mid-cavity HCM >>

d) Resting comprehensive transthoracic echocardiographic (TTE) study. (SC)

Cardiopulmonary exercise testing (CPET) with concomitant TTE. (SC) e)

f) Cardiac Magnetic Resonance Imaging (CMR). (SC)

8.5.2 Invasive pacing study (standard care denoted by SC, research activity denoted by RES)

a) Haemodynamic study performed for maximal pressure gradient across the mid-cavity with and without pacing from the RV apex, left middle cardiac vein, or both, sequentially. (SC)

b) For patients judged to be at significantly increased risk of sudden cardiac death, they will have a device with defibrillator functions as well as the pacemaker functions. Those thought not to be at significantly increased risk of sudden cardiac death may have a device with pacemaker functions only. PPM +/- ICD inserted at optimal settings of AV delay and lead polarity. (SC)

After one-day check as an inpatient to ensure proper PPM +/- ICD c) function, patient randomised in a double-blind, cross-over fashion. In one arm, the device will be set to the pacing mode "AAI", which is a backup pacing mode at 30 beats per minute, so it will therefore not be activated (non-active pacing). In the other, the device will be set to the pacing mode "DDD", with optimal atrio-ventricular delay as assessed during invasive haemodynamic study. This means it will pace almost all of the time (active pacing). Simultaneous Doppler echocardiography will be used to ensure the atrial component of LV filling is not truncated. (RES)

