8.6.7 Invasive haemodynamic pacing study in patient requiring PPM +/- ICD implant (SC)

a) Arterial access will be obtained by the Seldinger Technique from the right femoral artery (RFA) using a standard 7 French sheath. Venous access will be similarly obtained from the left subclavian or cephalic veins. The right atrial and right ventricular leads will be implanted as usual.

b) The coronary sinus will be intubated using a LV lead delivery guiding catheter. When necessary, coronary venous anatomy will be defined by balloon occlusion coronary sinus venography. The coronary veins will then be intubated with a deflectable quadripolar catheter or an angioplasty wire.

Intravenous heparin 5,000 units will be administered and the C) haemodynamic study performed. The LV apical pressures will be

measured with an end-hole pigtail catheter. The arterial pressure will be measured from the side arm of the RFA sheath. The pressure difference between LV and arterial pressures will be the mid-cavity gradient.

AV synchronous pacing will be performed from the right d) ventricular apex, right ventricular outflow tract, distal middle cardiac vein and posterior or lateral cardiac veins whilst measuring the respective LV gradients for 30 seconds before, during and after cessation of pacing.

If the best gradient reduction is achieved with LV pacing, a LV e) lead will be implanted with a biventricular device at the same sitting.

f) Following removal of the LV pigtail catheter, the activated clotting time will be checked. If it is more than 150 seconds, the heparin will be reversed with intravenous protamine sulphate.

g) The device will be programmed with the longest AV delay to allow continuous right or left ventricular pacing.

8.6.8 Invasive haemodynamic pacing study in patient with no other PPM +/- ICD indication or with an implanted dual chamber device (SC)

a) Arterial access will be obtained by the Seldinger Technique from the right femoral artery (RFA) using a standard 7 French sheath. Venous access will be similarly obtained from either the right femoral vein using two standard 7 French sheaths, or from the right femoral and right subclavian (assuming left sided device insitu) veins (depending upon the operator).

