8.9 Definition of End of Study

The end of the study is the last assessment of the last patient after 1 year of cross-over treatment and non-treatment arms (6 months of each).

| | Visit 1 | Visit 2 | Visit 3 | | Visit 4 |
|---|---------------------------|---------|----------------------------------|----------------|----------------------------------|
| Procedure | Pre-implant assessment | Implant | 24±4 weeks post implant | Cross- over | 48±4 weeks post implant |
| NYHA classification | x | | X | | X |
| SF36 & KCCM Questionnaire | x | | X | | X |
| CMR with stress perfusion | X | | | | |
| 6MW test | X | | X | | X |
| CPET with concomitant TTE | x | | X | | X |
| Randomisation | | x | | | |
| Device interrogation and programming at pacing clinic | | x | X | | X |
| Blood sample for BNP analysis | X | | X | | X |

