10. ETHICS

<<<<09/11/2017>> <<Pacemaker therapy for drug-refractory symptoms in mid-cavity HCM >>

Whilst we do not believe the study raises significant ethical issues, we have considered several ethical practicalities.

The treatments for patients with hypertrophic cardiomyopathy and mid-cavity obstruction to blood flow are very limited, but include medicines and cardiac transplant. The use of a pacemaker is an experimental treatment which has not yet been explored in a formal clinical trial.

We do not know which treatment method is generally better, which is why we are conducting the study. Participants will experience both a treatment period (pacing all the time) and a non-treatment period (very little pacing), before comparison of patient experience in both settings. The order in which the participant experiences each setting is not decided by their doctor or the research team, but by randomly assigning you to one or other first, like tossing a coin. Setting the pacemaker to pace all the time or pace very little will not affect the defibrillator function of the participant's device if it has one.

We have designed a clear and concise patient information sheet to explain this to prospective study participants, allowing them to make an informed choice as to whether to take part.

Another potential issue that the study raises is common to all cross-over design studies. If a participant has been randomised to be in the treatment arm first, and feels better (as we expect), and then switches to the nontreatment arm and feels symptomatically worse, they may not wish to continue the non-treatment arm. Because we don't know whether patients feel better due to the pacemaker setting, or simply just because they have undergone a procedure (placebo effect), it is necessary for the research participants to "cross-over" from one setting (treatment) to the other (nontreatment). Whilst this could be interpreted as withholding treatment from a patient, it should be stressed that it is not known whether one setting provides a benefit to the patient over another (when the patient is unaware of their treatment to mitigate against placebo effect).

Cross-over design studies are often considered the 'gold-standard' of medical research; however they are at risk of statistical impracticalities due to their

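### Patients with heart block can be randomised into a period of AAI at 30 bpm, a mode that gives no ventricular pacing if AV conduction fails

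*Protocol*

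**What the plan says.** - **Entry.** Protocol 7.1b lists, among the accepted reasons for device referral, "other indications such as heart block or obstructive physiology". It sets no limit on the degree of block, the escape rhythm or pacing dependence. The synopsis repeats the criterion.
- **Exclusions.** The only rhythm exclusion in 7.2 is item d, "Patients in atrial fibrillation at the time of implantation". Item g is a general discretionary clause: "Any patient not suitable in the clinician's opinion".
- **Patients who already have a device.** The heading of 8.6.8 also covers patients "with an implanted dual chamber device", without restricting why that device was implanted.
- **Programming.** Under 8.5.2c, a step marked as research activity, one arm is DDD with an optimised AV delay. The other is AAI, "which is a backup pacing mode at 30 beats per minute, so it will therefore not be activated (non-active pacing". No exception is given.
- **Ethics.** Section 10 offers one reassurance about the settings: "Setting the pacemaker to pace all the time or pace very little will not affect the defibrillator function". It defends the non-treatment period on the ground that "it is not known whether one setting provides a benefit to the patient over another".

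**The concern.** The statement that the AAI setting will not be activated holds for a patient whose AV conduction is intact. Inclusion 7.1b does not require that, and it names heart block as a route of entry. For a patient whose device was indicated for AV block, moving from DDD to AAI removes the treatment that the device was implanted to provide, and does so as a research step.

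The equipoise argument in Section 10 concerns whether pacing relieves obstruction and symptoms. It does not reach pacing indicated for heart block. The defibrillator reassurance does not address bradycardia, and 8.5.2b allows some patients to have a pacemaker-only device.

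What is at stake is mainly safety: severe bradycardia or asystole in an eligible patient during the non-active period. A secondary effect falls on the descriptive cross-over data. In such a patient the difference between DDD and AAI would partly reflect treatment of bradycardia rather than relief of mid-cavity obstruction.

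**Working it through.** The protocol gives no figure on this point to reproduce; its sample size calculation does not bear on it. The check sets the provisions side by side and then works out the length of exposure.

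**1. Can an affected patient reach the AAI period?**

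| Step | Provision | Stops a patient with high-grade AV block? |
|---|---|---|
| Inclusion | 7.1b | No; heart block is a named indication |
| Exclusion | 7.2a–f, h, i | No; none mentions AV block or pacing dependence |
| Exclusion | 7.2g | Only if a clinician chooses to use it |
| Check before randomisation | 8.5.2c, one-day inpatient check | No; its stated purpose is device function, not AV conduction |
| Programming | 8.5.2c | No; AAI at 30 bpm for all, no exception |
| Cross-over | 7.4, Section 10 | No; each participant is meant to spend a period in each setting |

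**2. What does the device do if conduction fails?** The longest interval between ventricular beats that the device itself permits is:
- ventricular backup at 30 bpm: 60 / 30 = 2.0 s;
- AAI at 30 bpm: no limit, because the ventricle is never paced. Any ventricular beat then depends on the patient's own escape rhythm.

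**3. How long is the exposure?**
- AAI first: 24 ± 4 weeks = 20 to 28 weeks (140 to 196 days).
- AAI second: the Schedule of Assessment puts the cross-over visit at 24±4 weeks and the final visit at "48±4 weeks post implant". Minimum (48 − 4) − (24 + 4) = 16 weeks (112 days); maximum (48 + 4) − (24 − 4) = 32 weeks (224 days).
- The scheme diagram in 7.4 labels the second period 24±4 weeks as well, which would be 20 to 28 weeks. The two sources differ at the extremes; the conclusion is the same under either.

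**4. How closely is the period watched?**
- Remote transmissions (8.5.3a) are three-monthly. Taking three months as 91 days, 112 / 91 = 1.2 and 224 / 91 = 2.5, so 1 to 3 fall in a period depending on timing.
- The DSMC (Section 11) reviews after every 4 patients. Assuming even recruitment of 25 patients over 28 months, 28 × 4 / 25 = 4.48 months, about 19.5 weeks.

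Planned review is therefore spaced on a scale similar to the exposure itself. A device in AAI 30 would also be working as programmed when it transmits.

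**5. Is an alternative available?** Right atrial and right ventricular leads are implanted under 8.6.7a. The active arm is DDD, so every randomised patient needs a working ventricular lead in any case.

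**The case against.** The strongest reply is that other text presumes intact conduction. The null hypothesis (6.2) compares pacing with sinus activation of the ventricle, and the acute study (8.6.7d) records gradients before and after pacing stops. A patient in persistent complete block could not supply that comparison, and the loss of conduction should show in the catheter laboratory before randomisation. This narrows the likely group, but it excludes no one explicitly and misses intermittent block or block that develops later.

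Second, 7.2g lets clinicians keep such patients out, and ECGs, remote transmissions, SAE reporting, urgent safety measures, DSMC and steering committee review and free withdrawal all exist. These reduce the risk. But 7.2g is discretionary and would have to override an indication that 7.1b invites; the other measures are monitoring or reaction, and none paces the ventricle.

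Third, the absence of a limit on degree of block in 7.1b, and on the earlier indication in 8.6.8, is silence rather than express permission, and the number affected could be zero. That is true. The participant information sheet may also disclose the risk, though disclosure would not supply pacing.

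Fourth, the remedy asks for a judgement on pacing dependence that the one-day check does not now include, and a ventricular backup mode could pace occasionally in the non-active period. Both are fair and are reflected in the fix.

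**Conclusion.** The concern stands and should be corrected before the plan is followed. The protocol admits patients with heart block, excludes none of them by rule, and assigns every randomised patient to a mode without ventricular pacing. For an affected patient the exposure is 20 to 28 weeks if AAI comes first and 16 to 32 weeks by the visit windows if it comes second (20 to 28 by the scheme diagram).

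The conclusion rests on the definition of AAI as atrial-only pacing and on reading 7.1b and 7.2 as written. It assumes no particular number of heart-block patients, because the protocol gives none. It is conditional on 7.2g not being used. The primary endpoint is not affected: Section 10 notes that it is collected before randomisation.

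**What to change.** Amend 8.5.2c in two places.

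1. **Who is randomised.** Add: *Patients with documented high-grade (second-degree type II or third-degree) AV block, or dependent on ventricular pacing at the one-day check, are not randomised and keep clinically indicated pacing. They may contribute to the acute study if an unpaced, intrinsically conducted recording exists.* Because they can still enter the acute primary analysis, 7.1 and 7.2 need not change.
2. **The non-active mode.** For all randomised patients, replace AAI 30 with a mode giving low-rate ventricular backup, for example VVI or DDI at 30 bpm. With intact conduction this should deliver little or no ventricular pacing, and it covers block that appears after the one-day check.

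Both parts are needed, since 30 bpm is a rescue rate and not treatment for established block.

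Report the ventricular pacing percentage for the non-active period descriptively, from the interrogation that closes it (visit 3 or visit 4 according to sequence). This shows whether the period was in fact unpaced. Exclude no patient on it after randomisation.

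**Cost.** One short amendment and no new visits, since interrogation is already scheduled at visits 3 and 4. The one-day check would also have to record underlying AV conduction. A few fewer patients may be randomised, which slightly reduces the feasibility data.
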